3.1 Study Design

This is a crossover study wherein each subject will serve as their own control. Comparisons will be made between the low choline diet periods to the 100% choline diet at the beginning and end of the 6 weeks on the three dietary intervals (see Fig. 1, Appendix).

Screening: Before entry to the study the participants will be seen at the University of North Carolina Nutrition Research Institute Outpatient Clinical facility where a physical exam by a physician and a Clinical Chemistry panel will be performed to ascertain that they are healthy. Subjects will have mass resonance spectroscopy to measure Cho compounds in liver, and mass resonance imaging to assess fatty liver to validate the isotope dilution methodology and Fibroscan technology, respectively.

Intervention: Recruited subjects will be asked to fill out the Automated Self-Administered 24-hour Dietary Assessment Tool (ASA24) found on the NCI web site (<https://epi.grants.cancer.gov/asa24/>) for 3 days the week prior to the first diet intervention. This will estimate the choline intake level for subjects beginning the study. The week after screening, subjects will be placed on one of the three dietary choline levels (100%, 50%, and 25% - order randomly assigned) with a minimum 2 week washout between. On day 12 of each diet period, subjects will receive a 250mg bolus dose of the Cho delivered as Cho-d9 in order to estimate Cho pool sizes by isotope dilution (see Fig. 1, Appendix).

Follow-up: If the clinical laboratory data remain within normal values, this will conclude the subject's participation. If not, see section 4.3 (below).

Unscheduled Visits: Subjects may have to make unscheduled visits to pick up food if their freezer storage space is limiting.

3.2 Allocation to Treatment Groups and Blinding (if applicable):

All subjects will be randomly assigned to the order of the diet interventions. Investigators making metabolite, MRI, MRS, or Cho pool analyses will be blinded to diet assignments.

3.3 Study Duration, Enrollment and Number of Subjects:

The study lasts 10 weeks and a few days for each subject. We plan to enroll 150 subjects: 50 males, 50 pre-menopausal females, and 50 post-menopausal females. We will recruit an additional 30 subjects to account for drop out replacement, so the total number of subjects is 180.

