3.4 Study Population

Inclusion criteria: Participants, ages 17 years - 70 years, will be recruited from the greater Kannapolis-Charlotte metro area (58% Caucasian, 33% African American; 3.5% Asian); we will make special efforts to assure that they reflect the race and ethnicity demographics of the region. Healthy men, pre- and post-menopausal women (defined as having had their last spontaneous menstrual bleeding >12 mo previously and as having a follicle stimulating hormone concentration >30 IU/L) and children (ages 17-18 years) will be asked to participate in a protocol approved by the Institutional Review Board at the University of North Carolina at Chapel Hill (n=60/group (we estimate that n=50/group will complete study) x 3 groups). Written informed consent will be obtained from all participants before initiating any study activities. Inclusion will be contingent on being in a good state of health as determined by physical examination and standard clinical laboratory tests with BMI <32.

Exclusion criteria: Subjects will be excluded if they are using drugs or medications known to be damaging to liver or muscle at typically prescribed doses or that have the potential to alter Cho metabolism (e.g., methotrexate); or if the volunteer has a history of hepatic, renal, or other chronic systemic disease. Individuals who are current smokers, who consume >2 alcoholic beverages/d or >14/wk, who are substance abusers or drug addicted, who are eating unusual diets that would interfere with the study, who have an allergy to soy (soy protein is used in experimental diet formulation), or people who are using Cho-containing dietary supplements are likewise ineligible.

Before entry to the study the participants will be seen at the University of North Carolina Nutrition Research Institute Outpatient Clinical facility where a physical exam by a physician and a Clinical Chemistry panel will be performed to ascertain that they are healthy.

For MRS and MRI testing, we will exclude subjects with: claustrophobia; cardiac pacemaker or artificial heart valve, metal plate, pin, or other metallic implant, intrauterine device, such as Copper-7 IUD, insulin or other drug pump, aneurysm clips, previous gunshot wound, cochlear implant or other hearing device, employment history as a metalworker (had metal in eye), permanent tattoos.

4 STUDY PROCEDURES (what will be done)

4.1 Screening/Baseline Visit procedures:

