score will be calculated based on the OPLS weights and the variability explained in OPLS-R. Biomarkers with $VIP > 1.5$ will be considered the most important biomarkers responsible for prediction. Pathway analysis will be performed using GeneGo metacore (Thomson Reuters, <https://portal.genego.com>) and QIAGEN's Ingenuity Pathway Analysis (IPA®, QIAGEN Redwood City, www.qiagen.com/ingenuity).

Statistical methods (SubAim 1c). Linear model with repeated measures will be used to identify SNPs that increase (or decrease) the risk for developing choline deficiency-induced organ dysfunction. This analysis will be performed for each diet period (healthy men, pre- and postmenopausal women) separately. In each linear model, the choline status score defined by Aim 1 is the response variable. Diet effect (fixed), genotype effect (fixed), subject effect (random) and diet \times genotype interaction effect are the independent variables. In the repeated measures design, each subject serves as his/her own control. Therefore, confounding effect from genotype is not our concern. However, it is possible that genotype serves as a moderator, which interacts with the diet effect, and affects the direction or strength of the diet effect. For example, the change in choline status score in responding to dietary choline may be observed in subjects with one genotype (responders), but not in subjects with other genotypes (non-responders). The genotypes that modify the diet effect will be identified by the diet \times genotype interaction term. This analysis will be performed in the MIXED procedure in SAS (SAS Institute, Inc., Cary, NC). Benjamini-Hochberg method for False Discovery Rate (FDR) correction will be used for multiple testing correction. To improve the normality of the data, data transformation such as log transformation will be applied to metabolomics data, and outliers with studentized residue > 3 or < -3 will be excluded. Post hoc comparisons will be performed to identify metabolites associated with different levels of dietary choline and different genotypes. The analysis described above will also be applied to choline pool size data to identify significant diet \times genotype interaction effect for choline pool size.

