6.4 Sample Size and Power

Sample size estimation (Aim 1, SubAim 1a,1b). Similar to OPLS-DA, OPLS-R is a multivariate method for prediction. Different from hypothesis testing methods such as t-test or ANOVA, where sample size is determined by the power of rejecting null hypotheses when the alternative hypothesis is true, the sample size of OPLS-R is determined by its accuracy of prediction. In this study, we propose to recruit three groups of subjects (healthy men, pre- and postmenopausal women) with $n=60$ /group (estimated that $n=50$ /group will complete study). We plan to analyze all three groups together ($n=50*3=150$ subjects) to identify a formula for composite score that can predict choline pool size for all three groups. In case the universal score does not perform well, we will analyze each group ($n=50$ subjects) separately. Using our previous data with $n=44$ subjects, we successfully identified a panel of metabolites that can be used to predict whether a sample is taken at baseline or after choline deficient diet. As shown by the ROC plot, the area under curve was 98.77%, which indicates very high sensitivity and specificity (Figure 2). Our previous study indicates that there is a strong association between the panel of biomarkers and choline status even when the model was developed with a relatively small number of samples.

Sample size estimation (SubAim 1c). This analysis will first be applied to the *PEMT* SNPs (rs12325817-C; rs4646343-A and rs3760188-A) that are known to interact with the effect of dietary choline in women but not in men (24). This analysis serves to confirm the consistency between the performance of the choline status score and existing knowledge. Assuming the effect size of the diet \times genotype interaction is 0.6 (moderate effect), we

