will have 89.61% of power to detect it at $P<0.05$ cutoff. The same analysis will then be performed for all other SNPs (>2 million) measured in this study. We will be under-powered for the global analysis after multiple testing adjustment for 2 million tests, so this analysis will be an exploratory analysis. To increase statistical power, we will use SNP based pathway enrichment analysis method (102). This analysis was developed for GWA studies, and addresses the lack of power issue in GWA studies. It will identify SNPs with jointly significant genetic effect, i.e. sharing the same biological pathways, even when the individual P value for each SNP may not be significant. The pathways identified from this analysis may provide insight into the regulation of choline metabolism.

7 STUDY INTERVENTION (drug, device or other intervention details)

Diets: The experimental diets, delivering 100%, 50% and 25% of the recommended intake of Cho (in all forms) (550 mg Cho/70 kg body weight/d), are identical except for the bread that we offer (Cho in the bread will be varied to deliver the desired Cho above that delivered by the base Cho diet as described previously (1)). The base Cho diet is composed of 0.8 g high biologic value protein/kg [current Recommended Dietary Allowance (RDA)], with 30% kcal coming from fat and the remaining kcal from carbohydrate; diets are prepared in-house to protocol specifications and are similar to those described in detail in a publication in JADA (1). These diets were designed to bracket the range of dietary intake observed in several large published human population studies (18-23, 75). We have experience using these limited Choline level diets for more than 60 days per subject in our previously published studies (10, 24, 25, 51, 55).

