8 STUDY INTERVENTION ADMINISTRATION

This is a crossover study wherein each subject will serve as their own control. Comparisons will be made between the low choline diet periods to the 100% choline diet at the beginning and end of the eight week period (see Fig. 1, Appendix). No randomization will take place as the study design requires all subjects start with a 100% Cho diet in order to compare biomarker changes to the graded decrease in Cho levels over subsequent weeks. All subjects will spend the last two weeks of the study on the 100% Cho replete diet.

Investigators making metabolite, MRI, MRS, metabolomics analyses, or Cho pool analyses, will be initially blinded to diet assignments. Only personnel performing work necessary for data interpretation leading to a publishable manuscript will be un-blinded.

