15 APPENDIX

Figure 1

Repeat the above for 50% Cho (275 mg/d) and 100% Cho (550 mg/d). Arms performed in random order with minimum 2 week washout in between.

Figure 1 outlines what each 2 week intervention period is comprised of. This will be completed 3 times per subject.

[figure not shown]
Figure 2

Figure 3

Pathway	Metabolite	Platform ²	Fatty liver		Muscle dysfunction		No dysfunction	
			D/B ¹	R/D ¹	D/B ¹	R/D ¹	D/B ¹	R/D ¹
Choline metabolism	Choline	T-LC/MS	0.67	1.50	0.66	1.25	0.71	NA
	Sarcosine	T-GC/MS	0.47	2.00	0.60	1.08	0.56	NA
	Dimethylglycine	T-GC/MS	0.51	1.81	0.55	1.41	0.59	NA
	Betaine	T-LC/MS	0.45	1.66	0.53	1.07	0.47	NA
	Methionine	T-GC/MS	0.86	1.10	0.93	1.01	0.96	NA
	Phosphatidylcholine (total)	T-LC/MS	0.89	1.08	0.90	1.06	0.97	NA
Carnitine metabolism	Homocysteine	T-GC/MS	1.16	0.97	1.19	0.99	1.27	NA
	Carnitine	N-LC/MS+	1.41	0.84	1.23	1.02	1.42	NA
	Butyrylcarnitine	N-LC/MS+	1.23	0.89	1.03	1.13	1.30	NA
	Isobutyrylcarnitine	N-LC/MS+	1.09	1.12	0.88	1.44	1.41	NA
	Isovalerylcarnitine	N-LC/MS+	0.75	1.36	1.01	0.88	0.87	NA
Renal transporter	Propionylcarnitine	N-LC/MS+	1.02	0.99	1.38	1.38	1.78	NA
	Hippurate	N-LC/MS+	0.53	1.88	0.93	0.72	0.75	NA
	3-indolepropionate	N-LC/MS+	0.74	1.03	1.08	0.62	0.50	NA
	CMPF	N-LC/MS-	0.46	0.86	0.57	0.74	0.32	NA
Keto acid metabolism	Creatinine	N-LC/MS+	1.00	0.95	1.00	1.00	1.12	NA
	Myo-inositol	N-GC/MS	0.70	1.22	0.85	1.13	0.76	NA
	Pyridoxate	N-LC/MS-	0.71	1.18	0.93	1.09	0.82	NA
Cell death	Erythronate	N-GC/MS	1.11	0.90	1.21	0.97	1.24	NA
	Urate	T-Clin Lab	1.19	0.90	1.39	0.92	1.22	NA
Amino acid metabolism	Pseudouridine	N-GC/MS	1.17	0.92	1.28	0.98	1.20	NA
	Glutamine	N-LC/MS+	1.07	0.87	1.06	0.98	1.12	NA
	Pyroglutamate	N-LC/MS-	1.29	1.06	1.08	1.03	1.36	NA
	Valine	N-LC/MS+	1.03	1.01	0.97	1.06	1.13	NA
	Glutamylvaline	N-LC/MS+	1.19	0.91	1.37	1.20	1.47	NA
	Glycine	N-GC/MS	1.12	0.89	1.09	0.98	1.09	NA
	Leucine	N-LC/MS+	1.01	1.03	0.87	1.45	1.25	NA
	Trans-4-hydroxyproline	N-GC/MS	1.01	1.35	0.70	0.89	1.18	NA
Diet	Stachydrine	N-LC/MS+	0.06	5.39	0.10	0.86	0.03	NA
Fatty liver	Ratio of liver fat to spleen fat	MRS	1.55	0.72	1.18	0.82	1.12	NA
	X - 02249	N-LC/MS-	0.63	1.60	0.57	0.98	0.67	NA
Unknown	X - 09789	N-LC/MS-	0.30	2.98	0.23	1.71	0.32	NA
	X - 11315	N-LC/MS+	0.82	0.95	1.03	0.92	0.84	NA

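### Does the 89.61% power quoted for the diet × genotype test in section 6.4 need to be recomputed because its inputs are not printed?

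*Combined protocol and SAP*

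**What the plan says.** Section 6.4, under SubAim 1c, takes the PEMT SNPs first. It assumes that the effect size of the diet × genotype "interaction is 0.6 (moderate effect") and concludes that the study "will have 89.61% of power to detect it" at P<0.05. Nothing else is attached to the figure.

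Other sections supply part of what is missing:

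- **Sample size.** The Aim 1 paragraph of section 6.4 gives 60 recruited and 50 completers per group. Section 3.4 agrees: "we estimate that n=50/group will complete study".
- **Unit of analysis.** Section 6.3 says of SubAim 1c: "This analysis will be performed for each diet period (healthy men, pre- and postmenopausal women) separately". The words in brackets show that the sex and menopausal groups are meant, so calling them diet periods is a slip. The model is a repeated-measures linear model with diet, genotype and their interaction, and a random subject effect, fitted in SAS MIXED.
- **Number of periods.** Section 3.1 compares diets "at the beginning and end of the 6 weeks on the three dietary intervals", and the note to appendix Figure 1 says of the two-week block: "This will be completed 3 times per subject".
- **A conflicting description.** Section 8 compares diets "at the beginning and end of the eight week period" and adds: "All subjects will spend the last two weeks of the study on the 100% Cho replete diet".

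On importance, section 6.2 lists SubAim 1c as the secondary endpoint, the synopsis says the study does not have to be powered for genotype differences, and section 10 defers genotyping to a later date.

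**The concern.** A power quoted to two decimals implies a definite calculation, yet an effect of 0.6 and a 5% level do not define one for a repeated-measures interaction. The answer depends on how many genotype classes there are, how many diets, whether 0.6 is a standardised difference or Cohen's f, and how strongly a person's visits are correlated.

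The suspicion grows when one searches for the source. A standard interaction F test with the protocol's own 50 completers returns 89.61% with three genotype classes and four diet periods. Four two-week periods would fit the eight weeks of section 8, but not the three diets of section 3.1. The figure might then belong to a design that is not being run.

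What is at stake is how a null result would be read. Section 6.4 uses the PEMT test to check that the choline status score agrees with existing knowledge. If no interaction appears, a reader will ask whether the score failed or the test was too weak, and only the power of the planned three-diet analysis helps with that.

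**Working it through.** **Inputs.** From section 6.4: effect 0.6, level 0.05, stated power 89.61%. From sections 6.3, 6.4 and 3.4: N = 50 completers when one group is analysed alone. From section 3.1 and appendix Figure 1: m = 3 diets. Not in the documents, and therefore assumed: k genotype classes, the scale of 0.6, the within-person correlation r, and the formula.

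**Formula.** For a within-subject interaction, df1 = (k−1)(m−1) and df2 = (N−k)(m−1). Power is the upper tail of a noncentral F with noncentrality λ beyond the central F 95% point. Conventions for λ differ. Reading 0.6 as Cohen's f gives λ = 0.36N. Reading it as a standardised difference gives f = 0.3 and λ = 0.09Nm/(1−r), or 0.09N/(1−r) where the factor m is omitted.

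**Step 1: reproduce the stated figure.** N = 50, k = 3, m = 4: df = (6, 141); λ = 0.36 × 50 = 18, or 0.09 × 50 × 4 = 18 with r = 0. Power = 0.89606, that is 89.61%. In a scan over k = 2–3, m = 2–5, N = 6–200 and six definitions of λ (2 × 4 × 195 × 6 = 9,360 set-ups), this is the only combination of N, k and m that rounds to 89.61%.

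**Step 2: what that scan held fixed.** Its definitions of λ allowed either no correlation adjustment or division by 0.5. The correlation is one of the unstated inputs, so it should be left free. Keep N = 50 and m = 3, and solve for the λ that gives 89.61%:

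| Classes | df | λ needed | Correlation that supplies it |
|---|---|---|---|
| 3 | (4, 94) | 16.01 | 0.09 × 50 × 3/(1−r) = 13.5/(1−r): r = 1 − 13.5/16.01 = 0.157 |
| 3 | (4, 94) | 16.01 | 0.09 × 50/(1−r) = 4.5/(1−r): r = 1 − 4.5/16.01 = 0.719 |
| 2 | (2, 96) | 12.89 | 4.5/(1−r): r = 1 − 4.5/12.89 = 0.651 |

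None of these correlations is impossible for repeated measurements on the same person. So three-diet set-ups at the study's own N reach the printed figure with two classes or with three.

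**Step 3: a simpler test also reaches it.** A two-sided two-sample t test with a standardised difference of 0.6 and 119 people split 52 v 67 (about 44%) gives 89.61%. That N is not a stated analysis size; it shows only how easily a two-decimal match arises.

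**Step 4: direction.** If the four-period calculation were the source, the same test with m = 3 would give 93.07% (λ = 18) or 83.17% (λ = 0.09 × 50 × 3 = 13.5). One is above 89.61% and the other below. Even on that supposition, the sign of the error depends on an undefined effect scale.

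**The case for a change.** The best argument for acting is that the omission is real and cheap to repair. The 89.61% cannot be rebuilt from section 6.4. Even granting that N = 50 can be inferred, the PEMT effect is expected in women only, so 50 (one group) or 100 (both groups of women) could be meant. The four-period match falls on the protocol's own completer number, and section 8 does describe an eight-week, non-randomised sequence at odds with section 3.1. Having chosen to print a power, the protocol ought to let a reader check it, especially where the test serves as a consistency check on the score.

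The missing inputs stand: they are absent, and listing them would improve the document. The inference about origin does not. The match is unique only while the correlation is held to two settings, and no document states three genotype classes; the only split of premenopausal women by PEMT response, in the genotyping part of section 5.1, is two-way (56% and 44%). Section 8 never mentions four periods: that number comes from dividing eight weeks by two. The conflict between sections 3.1 and 8 over the diet sequence is a separate matter. Those sections must be reconciled whatever the power figure's origin.

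**Conclusion.** No change to the plan follows. The 89.61% lacks documented inputs, but it is not shown to be wrong: at 50 completers, both three-period and four-period calculations reach it, and no shortfall in power has been demonstrated. The figures of 93.1% and 83.2% are conditional on an undocumented basis and should not replace it.

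The consequence is also small. The figure sets no enrolment number: the 50 per group appears in the Aim 1 sample-size paragraph, and the synopsis explicitly declines to power for genotype. The model, groups and diets for SubAim 1c are stated elsewhere, so the analysis would be run identically with or without the missing detail. A null PEMT result can be judged from the estimated interaction and its confidence interval, which say more than a planning figure.

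This conclusion assumes that SubAim 1c is analysed in one group at a time on three diets, and that the within-person correlation is genuinely open. The documents give no value for it. If the sponsor's records showed a calculation for a different number of diets, the figure should be restated; nothing in the documents establishes that.

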8 STUDY INTERVENTION ADMINISTRATION

This is a crossover study wherein each subject will serve as their own control. Comparisons will be made between the low choline diet periods to the 100% choline diet at the beginning and end of the eight week period (see Fig. 1, Appendix). No randomization will take place as the study design requires all subjects start with a 100% Cho diet in order to compare biomarker changes to the graded decrease in Cho levels over subsequent weeks. All subjects will spend the last two weeks of the study on the 100% Cho replete diet.

Investigators making metabolite, MRI, MRS, metabolomics analyses, or Cho pool analyses, will be initially blinded to diet assignments. Only personnel performing work necessary for data interpretation leading to a publishable manuscript will be un-blinded.

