Test Article(s) (If Applicable)	The experimental diets, delivering 100%, 50% (to be determined by a pilot study) and 25% of the recommended intake of Cho (in all forms) (550 mg Cho/70 kg body weight/d), are identical except for the bread that we offer (Cho in the bread will be varied to deliver the desired Cho above that delivered by the base 25% Cho diet as described previously (1)). On day 12 of a diet period, subjects will consume 250mg Cho in the form of Cho chloride (trimethyl-d9). We will confirm total Cho content of diets by LC-MS/MS analysis of samples of duplicate food portions as previously described (1).

Study Design	Healthy volunteers (n=50 males, 50 premenopausal females and 50 postmenopausal females; 30 additional subjects for dropout replacement), will be randomly assigned to an order of 2 week intervals of diets where they consume meals that we provide containing 100% of the recommended intake of Cho (550 mg Cho/day), 50% of the recommended intake of Cho (275 mg Cho), and 25% of the recommended intake of Cho (137.5 mg Cho) for 2 weeks each. Each dietary interval is followed by a minimum 2 week washout period. On day 12 of each diet period, subjects will consume a bolus of 250mg of Cho in the form of Cho chloride-(trimethyl-d9). Before this bolus, a plasma sample will be collected to measure baseline enrichment of Cho isotopes. At the end of each diet period, plasma and urine samples will be collected for biomarker assays and isotopic dilution estimation of Cho pool size, and we will perform transient elastography (Fibroscan) of liver to assess liver fat. (see Fig. 1, appendix).

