Subject Population key criteria for Inclusion and Exclusion:	
Inclusion Criteria
 
 1. Subjects age 17 – 70 years 2. Male & female; representative of the Kannapolis-Charlotte metro area 
Exclusion Criteria
 
 1. Implantable devices, BMI > 32, smokers, pregnant or planning to become, allergies to food to be consumed, chronic systemic diseases, consuming Cho-containing supplements, consuming drugs or medications known to cause liver or muscle damage or to alter Cho metabolism (e.g. methotrexate). For MRI/MRS we will exclude claustrophobia, pacemaker, artificial heart valve, metal plate, pin, or other metal implant, intrauterine devices such as Copper-7 IUD, insulin or other drug pump, aneurysm clips, previous gunshot wound, cochlear implant, or other hearing device, employment history as a metal worker, permanent (tattoo) eye-liner.
Number Of Subjects	180
Study Duration	Each subject's participation will last 6 weeks and a few days. This does not include the washout period between the dietary arms (minimum of 2 weeks each). The entire study is expected to last 4 years.
Study Phases	(1) Screening : screening will take place in years 1-3 with the goal of consenting 50 subjects per year to complete the study.
Screening	
Study Treatment	(2) Intervention : the study will take place in years 1-3. Subjects will be placed on diets as described in the study design (figure 1, app).
Follow-Up	

(3) Follow-up: year 4 of the study will involve data analysis and interpretation, and writing of a manuscript for publication.

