Efficacy Evaluations	
Expected Results and interpretation:
 
Our aim is to develop a panel of biomarkers and an algorithm for calculating a Cho status score that correlates well with measures of Cho pool size by isotope dilution. We will define the minimum set of biomarkers that provides >90% accuracy in predicting Cho pool size measured by isotopic dilution. We expect to see incremental declines in Cho status, as reflected in the panel of biomarkers. Results on the 100% diet should be similar to what we previously published. In the earlier studies, subjects were fed the 10% diet for a period of 2 to 7 weeks; in the proposed study, we feed 25%, 50%, and 100% (adequate intake) diets for two weeks (order randomly assigned) with 2 week washout periods in between. We expect that our results on the 25% & 50% diets will be less than those previously described; i.e. there will be smaller difference in the biomarkers than previously described. We expect that the 25% & 50% diets will show changes in Cho pool size and in biomarkers that fall between 100% and 10% values. Genotype will change the rate at which a diet treatment alters Cho pool size but will not affect whether our biomarker panel correlates with the pool size achieved. Thus, we do not have to power the study for genotype differences.

Pharmacokinetic Evaluations	N/A
Safety Evaluations	After each diet period a clinical chemistry panel will be run to assess potential liver and muscle damage. If any damage is noted after any of the dietary periods (liver damage = >1.5-fold increase in aspartate aminotransferase (AST) alanine transaminase (ALT) or muscle damage = >5-fold increase in creatine phosphokinase (CK)), affected subjects will follow the abnormal lab value protocol chart (See Appendix Figure 6). This will be reported to the IRB and the subject will be monitored and re-tested according to protocol and until AST/ALT and CK values return to normal.

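### Section 8 rules out randomisation and puts the 100% choline diet first and last over eight weeks, while the synopsis, Sections 3.1 and 3.2 and Figure 1 randomise the order of three diets

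*Combined protocol and SAP*

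**What the plan says.** Section 8 (Study Intervention Administration) describes a fixed sequence:

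- On allocation: "No randomization will take place as the study design requires all subjects start with a 100% Cho diet". The reason given is to relate biomarker changes to a stepwise reduction in choline over the following weeks.
- On the final period: "All subjects will spend the last two weeks of the study on the 100% Cho replete diet".
- On length and comparator, it compares the low-choline periods with the "100% choline diet at the beginning and end of the eight week period (see Fig. 1, Appendix").

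The rest of the protocol describes a randomised three-period crossover:

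- Synopsis, Study Design: subjects "will be randomly assigned to an order of 2 week intervals of diets", and "Each dietary interval is followed by a minimum 2 week washout period".
- Synopsis, Efficacy Evaluations: "diets for two weeks (order randomly assigned) with 2 week washout periods in between".
- Section 3.1 assigns the order of the 100%, 50% and 25% diets at random, with a washout of at least two weeks. Section 3.2 says that all subjects are randomised to diet order; it does not mention washout.
- Section 3.3 gives a duration of 10 weeks and a few days per subject.
- Section 4.2 schedules three arms (Visits 1-7, 8-14 and 15-21) and then ends participation.
- The text of Appendix Figure 1 has the arms in random order with washouts and the two-week block done three times per subject.

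The six weeks in the synopsis (Study Duration) do not conflict with this, because "This does not include the washout period between the dietary arms (minimum of 2 weeks each").

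Two other passages are unclear. Section 3.1 compares with the 100% diet at the start and end of the six diet weeks. Visit 1 in Section 4.2 supplies three days of 100% choline food without reference to the assigned order.

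**The concern.** The protocol both requires and forbids randomisation of diet order. Staff working from Section 8 would run a different allocation from staff working from Section 3.2, and allocation cannot be repaired once data are collected.

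Under the Section 8 sequence every subject meets a given diet level at the same point in time. Any trend over the study (season, adaptation, assay drift, accumulated effects of earlier diets) would then be mixed with the diet effect. This bears on the expectation stated in the synopsis, "We expect to see incremental declines in Cho status, as reflected in the panel of biomarkers", and on the diet effect in the SubAim 1c model of Section 6.3, which lists diet, genotype, subject and diet-by-genotype interaction but no period or time term.

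The reach is limited. The primary objective (Sections 2.1 and 6.3) is prediction of pool size by OPLS-R, not a diet contrast, and no effect on it is claimed here.

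**Working it through.** **Do the durations and period counts fit?**

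- Randomised design: 3 diets × 2 weeks = 6 weeks on diet, as in the synopsis. Adding 2 washouts × 2 weeks gives 10 weeks, which reproduces Section 3.3.
- Section 8: eight weeks is shorter than 10, so three diets with two washouts do not fit. Eight weeks does fit 4 × 2 = 8, that is, four consecutive diets without washout. The order 100-50-25-100 is inferred from this, because Section 8 does not list its periods. Four diets with three washouts would take 8 + 6 = 14 weeks.
- Three diets once each have 3! = 6 orders. Two start on 100%, two end on 100%, and none does both. No randomised three-diet order can meet Section 8.

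**What would the fixed order do to the diet contrasts?**

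Take 100-50-25-100 at times 1 to 4, subject effects, no time term, and a linear drift of *d* per period.

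- Mean time on 100% is (1 + 4)/2 = 2.5; on 50% it is 2; on 25% it is 3.
- Bias of 50% v 100%: (2 − 2.5)*d* = −0.5*d*.
- Bias of 25% v 100%: (3 − 2.5)*d* = +0.5*d*.
- Bias of 25% v 50%: (3 − 2)*d* = *d*.

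The documents give no drift. At an assumed *d* of 0.3 to 0.5 within-person SD, the contrasts with 100% are biased by 0.15 to 0.25 SD in absolute size, and 25% v 50% by 0.3 to 0.5 SD.

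**Can a time term repair it?**

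- With categorical period, the period-2 indicator equals the 50% indicator and the period-3 indicator equals the 25% indicator. The within-person design (two diet, three period and two interaction columns) has rank 5 for 7 columns. The diet main effects cannot be estimated; the diet-by-genotype interaction can.
- With a linear time term, the two 100% periods identify the slope as (y4 − y1)/3, with variance 2/9 at unit within-person SD. The linear bias is removed. The per-person SE rises from √1.5 = 1.225 to √(1.5 + 0.25 × 2/9) = 1.247 for a contrast with 100% (about 2%), and from √2 = 1.414 to √(2 + 2/9) = 1.491 for 25% v 50% (about 5%).

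**The interaction.** If drift is the same in both genotypes, the interaction bias is 0. If drift differs between genotypes by *e* per period, it is −0.5*e* and +0.5*e*.

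**Separate point: random order without a period term.**

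- In a random three-period order, two diets are one period apart in 4 of 6 orders and two apart in 2 of 6. The mean squared gap is (4 × 1 + 2 × 4)/6 = 2.
- At unit SD, the variance of a within-person contrast is therefore 2 + 2*d*², a factor of 1 + *d*². The SE rises by √1.09 − 1 ≈ 4% at *d* = 0.3 and √1.25 − 1 ≈ 12% at *d* = 0.5, before about 1% is deducted for the cost of the period term.
- Simulation agrees (5000 replicates; 28 v 22 people, from the 56%/44% split of premenopausal women in the Section 5.1 genotyping text applied to 50). The table gives the interaction SE for 25% v 100%:

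| Drift (SD per period) | Without period | With period | SE increase from omitting period |
|---|---|---|---|
| 0 | 0.396 | 0.401 | about −1% |
| 0.3 | 0.419 | 0.407 | about 3% |
| 0.5 | 0.450 | 0.406 | about 11% |

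Mean bias was at most 0.007 and type I error 4.7% to 5.1%. Under random order, omitting period costs precision, not validity.

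**The case against.** The strongest reply is that Section 8 is the outlier. Random order is stated in five places and its absence in one; Figure 1, which Section 8 cites, says random order; and the Section 4.2 visit schedule has no fourth arm for a return to 100%. This lowers the risk of staff following Section 8 but does not remove it. Nothing in the document marks Section 8 as superseded, it is the section on administering the intervention, it gives a reason for its rule, and the Visit 1 food text can be read as supporting it.

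The second reply is that the confounding is overstated. This is right in part: a linear time term would remove linear drift under the inferred order at a cost of about 2% to 5% in SE. The biases above apply to a model without a time term, as Section 6.3 is written, and non-estimability applies only to unrestricted period effects. The period order and drift sizes are also assumptions, and the expected decline in status is an expectation rather than a specified test.

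The third reply is that the period and previous-diet terms do not follow from the contradiction. That is fair. They are kept apart below: no carry-over evidence is offered, the randomised design already includes washout, and omitting period causes no material bias under random order.

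**Conclusion.** The contradiction holds and must be fixed. Section 8 conflicts with the synopsis, Sections 3.1 to 3.3 and Figure 1 on randomisation, first and last diet, and length, and no reading satisfies both. This conclusion rests on the text and the week counts alone, not on any drift value.

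The size of the statistical harm is conditional. If the order were 100-50-25-100 with linear drift of 0.3 to 0.5 within-person SD per period and no time term, the diet contrasts would be biased by 0.15 to 0.25 SD against 100% and 0.3 to 0.5 SD between 25% and 50%. The SubAim 1c interaction stays unbiased if drift is common to both genotypes.

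The missing period term under random order is a lesser matter of precision in a secondary analysis: about 3% and 11% in interaction SE at the two assumed drifts.

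**What to change.** Make all passages describe one allocation: Section 8 (randomisation, first and last diet, eight-week period), the Section 3.1 comparison at the start and end of six weeks, and the Visit 1 food text in Section 4.2. Which schedule applies is for the sponsor to state. This is a text change with no extra samples or assays.

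Separately, if the order is random, add period as a fixed effect to the SubAim 1c models for choline status score and pool size. It uses two degrees of freedom and costs about 1% in interaction SE if there is no drift. A previous-diet term should be a sensitivity analysis only. Added to the period model, it raises the diet-contrast SE by about 7% to 8% within one genotype (28 people) and 12% to 13% over all 50, and the interaction SE by about 1%.
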